7.4.1.1 Dose Delay Criteria for Special Population (Cohort A1)

All dose delay criteria listed in [Section 7.4.1](#) apply to the special population cohort, with the following exceptions for participants with hepatic and renal impairment:

- If a participant has Grade 2 baseline AST or ALT elevation (> 3.0 - $5.0 \times$ ULN), delay dosing for a two-fold increase in AST or ALT or for AST or ALT values $8 \times$ ULN.
- If a participant has Grade 2 baseline total bilirubin (> 1.5 - $3.0 \times$ ULN), delay dosing for drug-related elevation $> 5.0 \times$ ULN.
- If a participant has Grade 4 CrCl (CrCl < 15 ml/min), delay dosing/hold dose; participants may resume dosing with CrCl > 20 ml/min.

7.4.2 Dose Reductions

There will be no dose reductions for nivolumab or ipilimumab.

7.4.3 Treatment of Infusion Reactions

Since nivolumab and ipilimumab contain only human immunoglobulin protein sequences, they are unlikely to be immunogenic and induce infusion or hypersensitivity reactions. However, if such a reaction were to occur, it might manifest with fever, chills, rigors, headache, rash, pruritus, arthralgias, hypo- or hypertension, bronchospasm, or other symptoms. All Grade 3 or 4 infusion reactions should be reported within 24 hours to the BMS Medical Monitor and reported as an SAE if criteria are met. Infusion reactions should be graded according to National Cancer Institute (NCI) common terminology criteria for adverse events (CTCAE) (Version 4) guidelines.

Treatment recommendations are provided below and may be modified based on local treatment standards and guidelines, as appropriate:

For Grade 1 symptoms: (mild reaction; infusion interruption not indicated; intervention not indicated)

- Remain at bedside and monitor participant until recovery from symptoms. The following prophylactic premedications are recommended for future infusions: diphenhydramine 50 mg

(or equivalent) and/or acetaminophen/paracetamol 325 to 1000 mg at least 30 minutes before additional nivolumab or ipilimumab administrations.

For Grade 2 symptoms: (moderate reaction requires therapy or infusion interruption but responds promptly to symptomatic treatment [eg, antihistamines, non-steroidal anti-inflammatory drugs, narcotics, corticosteroids, bronchodilators, intravenous {IV} fluids]; prophylactic medications indicated for ≤ 24 hours)

- Stop the nivolumab or ipilimumab infusion, begin an IV infusion of normal saline (or diluent), and treat the participant with diphenhydramine 50 mg IV (or equivalent) and/or acetaminophen/paracetamol 325 to 1000 mg; remain at bedside and monitor participant until resolution of symptoms. Corticosteroid and/or bronchodilator therapy may also be administered as appropriate. If the infusion is interrupted, then restart the infusion at 50% of the original infusion rate when symptoms resolve; if no further complications ensue after 30 minutes, the rate may be increased to 100% of the original infusion rate. Monitor participant closely. If symptoms recur, then no further nivolumab or ipilimumab will be administered at that visit. Administer diphenhydramine 50 mg IV, and remain at bedside and monitor the participant until resolution of symptoms. The amount of study drug infused must be recorded on the electronic case report form (eCRF).
- For future infusions, the following prophylactic premedications are recommended: diphenhydramine 50 mg (or equivalent) and/or acetaminophen/paracetamol 325 to 1000 mg should be administered at least 30 minutes before nivolumab or ipilimumab infusions. If necessary, corticosteroids (up to 25 mg of SoluCortef or equivalent) may be used.

For Grade 3 or 4 symptoms: (severe reaction, Grade 3: prolonged [ie, not rapidly responsive to symptomatic medication and/or brief interruption of infusion]; recurrence of symptoms following initial improvement; hospitalization indicated for other clinical sequelae [eg, renal impairment, pulmonary infiltrates]. Grade 4: Life threatening; pressor or ventilatory support indicated)

- Immediately discontinue infusion of nivolumab or ipilimumab. Begin an IV infusion of normal saline (or diluent) and treat the participant as follows: Recommend bronchodilators, epinephrine 0.2 to 1 mg of a 1:1000 solution for subcutaneous administration or 0.1 to 0.25 mg of a 1:10,000 solution injected slowly for IV administration, and/or diphenhydramine 50 mg IV with methylprednisolone 100 mg IV (or equivalent), as needed. Participant should be monitored until the investigator is comfortable that the symptoms will not recur. Nivolumab or ipilimumab will be permanently discontinued. Investigators should follow their institutional guidelines for the treatment of anaphylaxis. Remain at bedside and monitor participant until recovery of the symptoms.

In case of late-occurring hypersensitivity symptoms (eg, appearance of a localized or generalized pruritus within 1 week after treatment), symptomatic treatment may be given (eg, oral antihistamine or corticosteroids).

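### Section 7.4.3 gives two conflicting instructions for infusion-reaction symptoms that recur after restart: withhold drug for that visit (Grade 2 text) or stop it permanently (Grade 3 text)

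*Combined protocol and SAP*

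**What the plan says.** Section 7.1 sends sites to Section 7.4.3 for the management of acute infusion reactions.

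Under Grade 2, that section tells the site to stop the infusion, treat, and "restart the infusion at 50% of the original infusion rate when symptoms resolve". It then covers failure of the restart: "If symptoms recur, then no further nivolumab or ipilimumab will be administered at that visit". Diphenhydramine 50 mg IV and bedside monitoring follow, and the amount infused goes on the eCRF. The next bullet begins: "For future infusions, the following prophylactic premedications are recommended".

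The Grade 3 or 4 paragraph comes directly afterwards. Its description of Grade 3 includes "recurrence of symptoms following initial improvement", and its required action is "Nivolumab or ipilimumab will be permanently discontinued". The opening of the section adds a reporting duty: "All Grade 3 or 4 infusion reactions should be reported within 24 hours to the BMS Medical Monitor".

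The discontinuation sections agree with the Grade 3 or 4 paragraph. Section 8.1.1.1 stops nivolumab for a Grade 3 drug-related infusion reaction, however short. Section 8.1.1.2 stops ipilimumab for bronchospasm or another hypersensitivity reaction of Grade 3 or higher, and for other Grade 3 non-skin drug-related events outside a short list of exceptions. Section 8.1.1.3 carries both sets of rules over to Cohort A1, with exceptions for hepatic impairment.

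**The concern.** Restart requires that symptoms have resolved, so symptoms that come back after restart have recurred after improvement. By the section's own description that is Grade 3. The Grade 2 text nevertheless deals with it as a Grade 2 matter: no more drug that day, an antihistamine, and then a bullet that assumes later infusions. Nothing tells the site to regrade.

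What is at stake is participant safety. The instruction is meant for use at the bedside, and the two readings lead to opposite decisions about the next dose. A site that keeps the event at Grade 2 also has no duty under Section 7.4.3 to tell the Medical Monitor within 24 hours, because that duty is confined to Grades 3 and 4.

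**Working it through.** No figure in the plan needs reproducing. The check is a comparison of the texts.

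| Question | Grade 2 text, 7.4.3 | Grade 3 or 4 text, 7.4.3 |
|---|---|---|
| Is recurrence after restart covered? | Yes, by name | Yes, as "recurrence of symptoms following initial improvement" |
| Further drug? | None for that visit | "Nivolumab or ipilimumab will be permanently discontinued" |
| Later infusions? | Premedication recommended; no exception for recurrence | None |
| Medical Monitor within 24 hours? | Not required | Required |

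1. **Same event.** The restart condition is "restart the infusion at 50% of the original infusion rate when symptoms resolve". Every recurrence reached through the Grade 2 path therefore follows improvement and meets the Grade 3 wording. No recurrence after restart falls under the Grade 2 text alone.

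2. **Consequence of a Grade 3 label.** Section 7.4.3 requires permanent discontinuation, and Section 8.1.1.1 requires it for nivolumab. For ipilimumab, Section 8.1.1.2 does not name infusion reactions. It reaches them through hypersensitivity or through the general Grade 3 non-skin rule, so a skin-only reaction is caught there only if it is classed as hypersensitivity. The Grade 3 or 4 paragraph of 7.4.3 names ipilimumab itself, so the conflict holds for both drugs.

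3. **Consequence of a Grade 2 label.** Section 7.4.1 asks for a delay for a Grade 2 non-skin drug-related event. Sections 7.4.5.1 and 7.4.5.2 let dosing resume once the event has settled to Grade 1 or baseline, subject to the usual dosing intervals. No grade-based rule then blocks the next dose.

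4. **Does another clause settle it?** The section says its treatment recommendations "may be modified based on local treatment standards and guidelines, as appropriate". That clause is about treating the reaction. It does not set aside the stopping rules in Section 8.1.1, and Section 9 rules out waivers and exemptions.

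**The case against.** The best defence is that the protocol already determines the right outcome. Section 7.4.3 calls for CTCAE version 4 grading, and the Grade 3 description is printed just below the Grade 2 bullets. On this reading the withholding sentence is only the immediate step, and the future-infusions bullet does not govern an event that has become Grade 3. A careful site would reach the correct decision. This stands as a reason to expect few errors. It does not reconcile the text: there is no instruction to regrade, the recurrence step is written with Grade 2 treatment, and the next bullet plans more infusions without excepting recurrence.

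There are also safeguards that do not depend on grade. Section 9 requires immediate safety concerns to be discussed with the sponsor straight away to decide whether treatment continues. Section 3.3 has the Medical Monitor reviewing safety continuously, including non-serious events. Sections 8.1, 8.1.1.1 and 8.1.1.2 let the investigator stop either drug on judgment. The eCRF entry makes an incomplete infusion visible. These checks are real and reduce the risk, but each relies on someone recognising the problem that the Grade 2 text obscures.

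Three stronger readings are tempting, and the documents do not support them:

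- *The acute reaction is undertreated.* The Grade 2 text itself says "Corticosteroid and/or bronchodilator therapy may also be administered as appropriate", and local modification of treatment is allowed.
- *Nothing would prevent re-dosing.* The safeguards above could.
- *The primary endpoint is biased by a known amount.* Hypersensitivity/infusion reaction is a select AE category of the primary endpoint, which counts Grade 3 to 5 events, so under-grading could lower that count. But the documents give no frequency of recurrence or of under-grading. One participant in 400 is 0.25 percentage points and one in 100 is 1.0 point; that is only the weight of one person, not an estimate. Section 3.1.1 states that there is no formal hypothesis, so no test is affected.

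**Conclusion.** The conflict is real and should be corrected. For recurrence after restart, Section 7.4.3 gives a dosing instruction that contradicts its own Grade 3 description and the stopping rules in Section 8.1.1. A site that follows the Grade 2 text literally could re-dose a participant who is required to stop.

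Its size cannot be stated. The documents offer no recurrence rate, and Section 7.4.3 describes such reactions as unlikely. The conclusion rests on two readings of the text: that restart presupposes resolution, and that the Grade 3 description means what it says. It also assumes the reaction is drug-related, as the rules in 8.1.1.1 require. It does not depend on any site having made the error. This is an inconsistency in a safety instruction, not a flaw in the analysis.

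**What to change.** At the next protocol revision, in the Grade 2 part of Section 7.4.3:

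- Replace the sentence "If symptoms recur, then no further nivolumab or ipilimumab will be administered at that visit" and the diphenhydramine sentence that follows it with: *If symptoms recur after restart, stop the infusion, regrade the event as Grade 3, report it to the Medical Monitor within 24 hours, manage it under the Grade 3 or 4 paragraph, and permanently discontinue per 8.1.1.1 and/or 8.1.1.2.* Both sentences have to go; otherwise Grade 2 treatment would sit beside an instruction to manage the event as Grade 3 or 4.
- Keep the sentence on recording the infused amount on the eCRF.
- Limit the future-infusions bullet to Grade 2 reactions without recurrence.

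The reference to 8.1.1.1 and 8.1.1.2 keeps the existing rules on which drug stops: separate assessment of each drug, both stopped if attribution is unclear, and no ipilimumab after nivolumab has been discontinued. If the sponsor wants some mild recurrences to stay at Grade 2, it should say which ones and amend the Grade 3 description to match.

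The cost is two replaced sentences and one qualifier, with no new data collection. Because a dosing instruction changes, it belongs in a protocol revision with IRB/IEC approval under Appendix 2. The downside is that a few participants with mild recurrences will stop the drug, which the Grade 3 description already requires.

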7.4.4 Management Algorithms for Immuno-Oncology Agents

Immuno-oncology (I-O) agents are associated with AEs that can differ in severity and duration than AEs caused by other therapeutic classes. Nivolumab and ipilimumab are considered immuno-oncology agents in this protocol. Early recognition and management of AEs associated with immuno-oncology agents may mitigate severe toxicity. Management Algorithms have been developed to assist investigators in assessing and managing the following groups of AEs:

- Gastrointestinal
- Renal
- Pulmonary
- Hepatic
- Endocrinopathy
- Skin
- Neurological

The above algorithms are found in both the nivolumab and ipilimumab Investigator Brochures, as well as in [Appendix 7](#).

Additionally, rare cases of myotoxicity (myositis, myocarditis, and rhabdomyolysis), some with fatal outcome, have been reported with nivolumab or nivolumab in combination with ipilimumab. If a patient develops signs and symptoms of myotoxicity, close monitoring should be implemented, and the patient referred to a specialist for assessment and treatment without delay. Based on the severity of myotoxicity, nivolumab or nivolumab in combination with ipilimumab should be withheld or discontinued, and appropriate treatment instituted. For grade 3 myocarditis, nivolumab or nivolumab in combination with ipilimumab should be permanently discontinued.

7.4.5 Criteria to Resume Dosing

7.4.5.1 Criteria to Resume Nivolumab for Cohorts A, B, and C

Participants may resume treatment with nivolumab when the drug-related AE(s) resolve(s) to Grade \leq 1 or baseline, with the following exceptions:

- Participants may resume treatment in the presence of Grade 2 fatigue.
- Participants who have not experienced a Grade 3 drug-related skin AE may resume treatment in the presence of Grade 2 skin toxicity.
- Participants with baseline Grade 1 AST/ALT or total bilirubin who require dose delays for reasons other than a 2-grade shift in AST/ALT or total bilirubin may resume treatment in the presence of Grade 2 AST/ALT OR total bilirubin.
- Participants with combined Grade 2 AST/ALT and total bilirubin values meeting discontinuation parameters ([Section 8.1](#)) should have treatment permanently discontinued.
- Drug-related pulmonary toxicity, diarrhea, or colitis must have resolved to baseline before treatment is resumed. Participants with persistent Grade 1 pneumonitis after completion of a

steroid taper over at least 1 month may be eligible for retreatment if discussed with and approved by the BMS Medical Monitor.

- Participants who received systemic corticosteroids for management of any drug-related toxicity must be off corticosteroids or have tapered down to an equivalent dose of prednisone ≤ 10 mg/day.

Participants with drug-related endocrinopathies adequately controlled with only physiologic hormone replacement may resume treatment after consultation with the BMS Medical Monitor (or designee). Adrenal insufficiency requires discontinuation regardless of control with hormone replacement.

Dose delay of nivolumab which results in treatment interruption of > 6 weeks requires treatment discontinuation, with exceptions as noted in [Section 8.1.1](#).

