7.4 Dosage Modification

7.4.1 Dose Delay Criteria for Cohorts A, B, and C

Nivolumab and ipilimumab administration should be delayed for the following:

- Grade 2 non-skin, drug-related AE, except for fatigue
- Grade 3 skin, drug-related AE
- Grade 2 drug-related creatinine, AST, ALT and/or total bilirubin abnormalities
- Grade ≥ 3 drug-related laboratory abnormality, with the following exceptions:
 - Grade 3 lymphopenia or asymptomatic amylase or lipase does not require a dose delay
 - Grade ≥ 3 AST, ALT, Total Bilirubin will require dose discontinuation
- Any AE, laboratory abnormality or inter-current illness which, in the judgment of the investigator, warrants delaying the dose of study medication.
- Participants receiving ipilimumab in combination with nivolumab that have drug-related toxicities that meet the criteria for dose delay, should have both drugs (ipilimumab and nivolumab) delayed until retreatment criteria are met. (Exceptions apply to the retreatment criteria after dose delay of ipilimumab and nivolumab for Grade 4 amylase and lipase abnormalities that are not associated with symptoms or clinical manifestations of pancreatitis and that are attributed to ipilimumab alone.)

Participants who require delay should be re-evaluated weekly or more frequently if clinically indicated and resume study medication dosing when re-treatment criteria are met.

Rescheduling:

- Nivolumab may be delayed until the next planned ipilimumab dose if the next ipilimumab dose is scheduled within the next 12 days. This will permit periodic ipilimumab dosing to be synchronized with nivolumab dosing.

- Ipilimumab should be dosed at the specified interval regardless of any delays in intervening nivolumab doses. However, in order to maintain periodic synchronized dosing of ipilimumab and nivolumab, the dosing days of nivolumab and ipilimumab may be adjusted within the permitted ± 5 day window, as long as consecutive nivolumab doses are given at least 12 days apart. Ipilimumab may be delayed beyond the 5 day window if needed to synchronize with the next nivolumab dose.
- If an ipilimumab dose is delayed beyond 6 weeks from the prior ipilimumab dose, then subsequent ipilimumab doses should be rescheduled to maintain the 6 week interval between consecutive ipilimumab doses.
- A dose delay of ipilimumab which results in no ipilimumab dosing for > 12 weeks requires ipilimumab discontinuation, with exceptions as noted in [Section 8.1.1.2](#).

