7.4.5.2 Criteria to Resume Ipilimumab for Cohorts A, B, and C

Participants may resume treatment with nivolumab and ipilimumab when drug-related AE(s) resolve(s) to Grade 1 or baseline value, with the following exceptions:

- Participants may resume treatment in the presence of Grade 2 fatigue.
- Participants who have not experienced a Grade 3 drug-related skin AE may resume treatment in the presence of Grade 2 skin toxicity.
- Participants with baseline Grade 1 AST/ALT or total bilirubin who require dose delays for reasons other than a 2-grade shift in AST/ALT or total bilirubin may resume treatment in the presence of Grade 2 AST/ALT or total bilirubin.
- Participants with combined Grade 2 AST/ALT and total bilirubin values meeting discontinuation parameters ([Section 8.1](#)) should have treatment permanently discontinued.
- Drug-related pulmonary toxicity, diarrhea, or colitis must have resolved to baseline before treatment is resumed.
- Participants who received systemic corticosteroids for management of any drug-related toxicity must be off corticosteroids or have tapered down to an equivalent dose of prednisone ≤ 10 mg/day.
- Drug-related endocrinopathies (except Grade 3 or greater adrenal insufficiency) adequately controlled with only physiologic hormone replacement may resume treatment after consultation with the BMS Medical Monitor
- Dose delay of ipilimumab which results in no ipilimumab dosing for > 12 weeks requires ipilimumab discontinuation, with exceptions as noted in [Section 8.1.1.2](#).
- Ipilimumab may not be resumed sooner than 37 days after the prior ipilimumab dose.
- In general, participants who meet criteria to resume ipilimumab will also have met criteria to resume nivolumab, so it should be feasible to synchronize dosing of both drugs when resuming ipilimumab. In order to facilitate this, the dosing days of nivolumab and ipilimumab may be adjusted within the permitted ± 5 day window, as long as consecutive nivolumab doses are given at least 12 days apart.

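### A drug-related liver hold can be lifted with no fall in the liver value: same-test Grade 1 to Grade 2 rises in all cohorts, and doubled AST/ALT up to 8 x ULN in part of Cohort A1

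*Combined protocol and SAP*

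**What the plan says.** **All cohorts.** Section 7.4.1 lists among its reasons to delay both drugs "Grade 2 drug-related creatinine, AST, ALT and/or total bilirubin abnormalities", with no qualifier for baseline grade. Participants are re-evaluated at least weekly and "resume study medication dosing when re-treatment criteria are met". At Grade 3 or above, the same section says "AST, ALT, Total Bilirubin will require dose discontinuation".

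Section 7.4.5.1 (nivolumab) makes recovery of the drug-related event to Grade 1 or less, or to baseline, the default for restarting. It then excepts participants with Grade 1 AST/ALT or bilirubin at baseline "who require dose delays for reasons other than a 2-grade shift in AST/ALT or total bilirubin may resume treatment in the presence of Grade 2" liver values. Section 7.4.5.2 (ipilimumab) has the same exception: such participants "may resume treatment in the presence of Grade 2 AST/ALT or total bilirubin".

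**Cohort A1.** Section 7.4.1.1 says the delay criteria of 7.4.1 "apply to the special population cohort, with the following exceptions for participants with hepatic and renal impairment". Its liver exceptions concern Grade 2 baselines only. For baseline AST/ALT above 3.0 to 5.0 x ULN it says "delay dosing for a two-fold increase in AST or ALT or for AST or ALT values" of 8 x ULN, printed without a comparison sign. Section 7.4.5.3 carries the restart rules over to A1. It adds that a participant with Grade 2 baseline AST/ALT, delayed for any reason except a drug-related value above 8 x ULN, may restart at 8 x ULN or below.

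**The concern.** A hold for toxicity protects the participant only if the restart rule asks for something that was not already true when the hold began. Here two sets of dosing rules meet on the same laboratory value and give opposite answers. Section 7.4.1 ends the delay by pointing to the restart criteria, so those criteria decide.

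At stake is re-dosing with both agents while a drug-related Grade 2 liver value is unresolved or, in A1 participants with hepatic impairment, while AST or ALT is still twice an already abnormal baseline. Because restarting is permitted rather than required, sites can also treat identical participants differently. Hepatitis is one of the named select adverse events (Section 4), and the study has no data monitoring committee (Section 5.1.2), so the written dosing rules are a main safeguard.

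**Working it through.** The plan gives no figure to reproduce. The check sets the hold and restart rules side by side.

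**Inputs.** Section 7.4.1.1 gives the Grade 2 bands: AST/ALT above 3.0 to 5.0 x ULN, bilirubin above 1.5 to 3.0 x ULN. Grade 1 is taken as above ULN up to those lower bounds (an assumption). Such baselines are eligible: for Cohorts A, B and C, Section 6.2 excludes only AST/ALT above 3.0 x ULN and bilirubin above 1.5 x ULN, with an allowance for Gilbert syndrome.

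**(a) Participant with at least one liver test at Grade 1 at baseline; isolated drug-related rise**

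| Baseline grade of the test that rises | On-treatment grade | Shift | Section 7.4.1 | Restart exception |
|---|---|---|---|---|
| 1 | 2 | 2 − 1 = 1 | delay | available, Grade 2 still present |
| 0 (normal) | 2 | 2 − 0 = 2 | delay | not available; default recovery rule governs |
| 1 | 3 | 3 − 1 = 2 | discontinue | not available |

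The first row is the defect. On a grid of Grade 1 baselines and Grade 2 on-treatment values for the same test, 800 of 800 AST/ALT pairs and 300 of 300 bilirubin pairs met the hold and the restart exception together. An example of the second row is baseline Grade 1 ALT with normal bilirubin, where bilirubin rises to Grade 2. The third row has a qualification: Section 8.1.1.1 lets some Grade 3 AST/ALT cases continue after discussion with the Medical Monitor.

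The isolated values covered are therefore AST or ALT above 3.0 to 5.0 x ULN with bilirubin at most 1.5 x ULN, or bilirubin above 1.5 to 3.0 x ULN with AST/ALT at most 3.0 x ULN. In each case the test that rose must have been Grade 1 at baseline. A1 participants with Grade 1 baselines fall under the same rules.

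**(b) Cohort A1, baseline AST/ALT of b x ULN, on-treatment value v**

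- Hold: v ≥ 2b, reading a two-fold increase as reaching twice baseline.
- Restart allowed: v ≤ 8.
- Overlap: 2b ≤ v ≤ 8, of width 8 − 2b, which exists only when b ≤ 4.0.

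| b | 2b | Overlap (x ULN) | Width |
|---|---|---|---|
| 3.1 | 6.2 | 6.2 to 8.0 | 1.8 |
| 3.5 | 7.0 | 7.0 to 8.0 | 1.0 |
| 3.75 | 7.5 | 7.5 to 8.0 | 0.5 |
| 4.0 | 8.0 | single point | 0 |
| 4.25 | 8.5 | none | – |

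A 0.01 x ULN grid gave the same limits: baselines 3.01 to 4.00, values 6.02 to 8.00. By value, this is (4 − 3)/(5 − 3) = 50% of the 3 to 5 x ULN entry range in Section 6.1.1; it is not a share of participants. The A1 AST/ALT stopping limits in Section 8.1.1.3 (above 10 x ULN for more than 2 weeks, or above 15 x ULN) lie beyond the overlap. The missing comparison sign matters only at exactly 8.

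**Contrast.** For A1 baseline Grade 2 bilirubin, the hold is for drug-related values above 5.0 x ULN, and the restart exception stops at 5.0 x ULN. The two rules match, and there is no overlap.

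**Conditions that remain.** These are re-evaluation at least weekly, steroids at or below 10 mg/day prednisone equivalent, the stop for combined AST/ALT and bilirubin elevation, 12 days between nivolumab doses, the rule that "Ipilimumab may not be resumed sooner than 37 days after the prior ipilimumab dose", and investigator judgment. None requires an isolated liver value to fall.

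**The case against.** The strongest reply is that this is a tolerable design choice. A one-grade move from an already abnormal baseline may be acceptable. Restarting is permissive, investigators may delay for any laboratory abnormality, and a persisting Grade 2 value still meets the 7.4.1 trigger at the next dose. The Medical Monitor also reviews A1 safety monthly until the cohort has been fully enrolled and followed for at least 3 months. All of that stands, and sites can comply with both sections. But if tolerance was intended, 7.4.1 lacks the matching baseline exception. If the exception was meant only for holds with non-liver causes, it does not say so: it removes only 2-grade shifts.

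The Hepatic Adverse Event Management Algorithm (Appendix 8) may contain recovery guidance. Its figure is not visible in the text reviewed, so this cannot be excluded. The appendix describes the algorithms as guidance, and they do not alter the wording of 7.4.5.1 to 7.4.5.3.

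Part (b) depends on how two-fold is read. If it means a rise by twice baseline, the hold starts at 3b, which exceeds 9 x ULN for every b above 3.0, and the overlap vanishes. Reaching twice baseline is the ordinary sense. Part (a) does not depend on it.

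A reader might infer that every isolated Grade 2 liver hold in participants with a Grade 1 baseline is undone. The text does not support that: the exception also removes 2-grade shifts, so a test that was normal at baseline and rises to Grade 2 falls back on the default recovery rule.

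**Conclusion.** The rules are wrong as written and worth fixing. In all four cohorts, a drug-related rise from Grade 1 to Grade 2 in the same liver test should be held, yet it already meets the liver condition for restarting. In Cohort A1 the same happens to the two-fold AST/ALT hold for baselines above 3.0 to 4.0 x ULN and values from twice baseline to 8 x ULN. The A1 baseline Grade 2 bilirubin rules are sound.

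The size in participants is unknown. The documents give no rate of baseline Grade 1 or drug-related Grade 2 liver values, and they do not state the size of the A1 hepatic subgroup. It would be tempting to cite 400 + 400 + 100 + 200 = 1,100 planned treated participants, but that is the whole trial, not the affected group. Nor do the documents support saying that restart is unconditional or that the primary endpoint is affected. Cohort A1 is exploratory.

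The conclusion rests on the literal text, on the Grade 1 bands assumed above and, for part (b), on reading two-fold as twice baseline.

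**What to change.** 1. In 7.4.5.1 and 7.4.5.2, limit the baseline Grade 1 exception to delays for reasons other than a drug-related AST, ALT or bilirubin elevation. State that a drug-related Grade 2 liver value that caused the delay must return to Grade 1 or less, or to baseline, before dosing restarts. If a shift-based rule is intended, instead add to 7.4.1 a matching exception for a test that was itself Grade 1 at baseline.
2. In 7.4.5.3, exclude delays caused by a two-fold AST/ALT rise from the exception. After such a delay, allow restart only when AST and ALT are both below twice baseline and no higher than 8 x ULN. The ceiling is needed because twice baseline exceeds 8 x ULN once baseline exceeds 4.0. Leave the handling of drug-related values above 8 x ULN unchanged.
3. Leave the A1 baseline Grade 2 bilirubin rules unchanged.

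The cost is a wording amendment to three subsections (or to 7.4.1 and 7.4.5.3) and a site letter, with no new data, visits or participants. The clinical cost is some longer holds. Nivolumab must stop when a delay exceeds 6 weeks from the previous dose. With the next dose due at day 14, that leaves 42 − 14 = 28 days, or about four weekly re-evaluations, for the value to recover. A few participants with a persistent drug-related elevation may reach that limit; Section 8.1.1.1 exempts only prolonged steroid tapers and approved delays that are not drug-related. For ipilimumab the margin is 84 − 42 = 42 days after the due dose.
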